Statistical Analysis Plan for Serum Assessment of Preterm Birth-- Outcomes Compared to Historical Controls: AVERT PRETERM TRIAL

ClinicalTrials.gov number: NCT03151330

Lead Study Investigator(s): [name], MPH-ChristianaCare

Funding: Sera Prognostics, Inc., ChristianaCare Health Services.

Title: Serum Assessment of Preterm Birth:
Outcomes Compared to Historical Controls: AVERT
PRETERM TRIAL

Study Design: Prospective cohort study of screened women compared to a historical control.

Study Objective: To examine whether the women who are screened using the PreTRM® test around 20 weeks gestation will have a statistically significant reduction in adverse pregnancy outcomes.

Prepared by: [name]
[name], MPH

TABLE OF CONTENTS

1. ACRONYMS and ABBREVIATIONS.....	3
2. Abstract.....	5
3. Statement of Problem and Study.....	7
3.1. Background and Rationale.....	7
3.2 Risk Identification.....	7
3.3. Study Design.....	8
3.4. Study Population.....	9
3.5. Primary Hypothesis or Question.....	10
3.6. Secondary Hypothesis or Question.....	10
3.7. Definitions of Outcomes.....	10
4. Determination of Sample Size.....	12
5. Statistical Analysis.....	14
5.1. Analysis Population.....	14
5.2. Descriptive Statistics.....	15
5.3 Covariate Analyses.....	16
5.4 Primary and Secondary Analyses.....	19
5. Primary Endpoints.....	20
5.6. Secondary Endpoints.....	22
5.7. Exploratory Endpoints.....	23
5.8. Safety Analysis.....	29
5.9. Subgroup Analysis.....	29
5.10. Missing Data.....	30
6. Bias in the Hybrid Study.....	31
6.1 Potential bias in the hybrid study.....	32
6.2 Differences between historical and prospective cohorts.....	32
REFERENCES.....	32

1 ACRONYMS and ABBREVIATIONS

ACOG	American College of Gynecologists
AE	Adverse Event
AFI	Amniotic fluid index
APS	Antiphospholipid syndrome
ASA	Acetylsalicylic acid
AUC	Area under the curve
BPD	Bronchopulmonary dysplasia
BPP	Biophysical profile
CC	Cubic Centimeter
CCHS	ChristianaCare Health System
CL	Cervical Length
CLASI	Community Legal Aid Society, Inc
CLASP	Collaborative Low-dose Aspirin Study in Pregnancy
CRF	Case report form
CRL	Crown rump length
DCC	Data Coordinating Center
dL	Deciliter
DMS	Data Management System
EAGER	Effects of Aspirin in Gestation and Reproduction Study
EDD	Estimated due date (or estimated date of delivery)
FDA	U.S. Food and Drug Administration
g	Gram
GA	Gestational age
GAB	Gestational age at birth
GC	Gonococcus
ICER	Incremental Cost Effectiveness Ration
IRB	Institutional Review Board
IBP4	Insulin-like growth factor binding protein 4
ITT	Intention to treat
IVH	Intraventricular hemorrhage
LBW	Low birth weight
LC-MS/MS	Liquid chromatography –tandem mass spectrometry
LDA	Low dose aspirin
LMP	Last menstrual period
mg	Milligram
miPTB	Medically-indicated preterm birth
mm	Millimeter
NEC	Necrotizing enterocolitis
NICHD	Eunice Kennedy Shriver National Institute of Child Health and Human Development
NICU	Neonatal Intensive Care Unit
NIH	National Institutes of Health
NMI	Neonatal morbidity and mortality

NNOLOS	Length of neonatal hospital stay (NNOLOS)
NICULOS	Length of neonatal NICU stay (NICULOS)
OHRP	Office of Human Research Protections
P	Probability Value
PECEP	Pesario Cervical para Evitar Prematuridad
PTL	Preterm Labor
PROM	Premature rupture of membranes
PPROM	Preterm premature rupture of membranes
PTB	Preterm birth
PVL	Periventricular leukomalacia
RCT	Randomized Clinical Trial
RDS	Respiratory distress syndrome
RR	Relative Risk
SAE	Serious adverse event
SAB	Spontaneous Abortion
SCF	Specimen Collection Form
SD	Standardized Deviation
SEAR	Statistical analysis plan for health economic analysis of AVERT PTB
SGA	Small for gestational age
SHBG	Sex hormone binding globulin
SOP	Standardized Operating Procedure
SPTB	Spontaneous preterm birth
TOPS	a randomized Trial of Pessary in Singletons
TVCL	Trans-vaginal cervical length
TVUS	Trans-vaginal ultrasound
UAE	Unexpected Adverse Event
UTI	Urinary Tract Infection
VLBW	Very low birth weight
WHO	World Health Organization
17-OHPC	17-hydroxy progesterone caproate

2. Abstract

Executive Summary:

AVERT PRETERM is a historically controlled trial to evaluate the safety and efficacy of a preterm birth (PTB) prevention strategy versus standard-of-care pregnancy management in reduction of the incidence of adverse pregnancy outcomes. Subjects in the prospective arm receive a commercially-available laboratory developed test, PreTRM® (Sera Prognostics, Inc). Those with higher-risk results are offered a multimodal intervention protocol; the remainder receive routine pregnancy management. Outcomes are compared between the prospective arm and historical controls.

The AVERT study addresses an enormous obstetrical problem having a large unmet need with the use of a novel risk assessment tool (PreTRM®) and established multimodal interventions administered within the single ChristianaCare hospital network. However, there are several potential limitations to the AVERT study. Comparisons to historical controls can be susceptible to selection bias and epoch effects. Subjects who don't accept interventions may add self-selection bias. As well, AVERT is subject to a research halt due to the spread of SARS-CoV-2, avoiding a pandemic epoch effect while restricting study size.

This statistical analysis plan addresses the study objective of evaluation of the PTB prevention strategy while overcoming potential study limitations. The original endpoints are replaced with more powerful endpoints aligned to the study size and faithful to the study's goal of reducing adverse outcomes. The primary analysis is in a modified ITT population enabling comparison of the fully consented PTB prevention strategy population to a population who received standard care. To adjust for any bias in consent to intervention, exploratory analyses compare subjects accepting and not accepting interventions, and address the efficacy of individual intervention components.

An estimated 1,453 prospective subjects reached a gestational age of $37^{0/7}$ weeks before local spread of SARS-CoV-2 in Delaware and the associated shut-down of non-COVID-19 research at ChristianaCare. Approximately 10,000 historical controls were selected

from a period of about 2 years immediately prior to study initiation. The study design shows at least 86% power for 5% alpha shared across two co-primary endpoints: neonatal morbidity and mortality index and neonatal length of total hospital stay.

The funder, Sera Prognostics, will remain blinded to all clinical data until a formal communication of topline results from this analysis is made.

Background: Preterm birth (PTB) remains the leading cause of neonatal mortality and long term disability throughout the world. Recently treatments early in pregnancy such as progesterone, cervical support and maternal support have been demonstrated to delay delivery amongst at risk women. Nonetheless, the majority of women who are at risk are not identified using current screening modalities.

Hypothesis: A cohort of pregnancies who are screened using the PreTRM® test around 20 weeks gestation in which a bundle of interventions is given for elevated PreTRM® risk will show either decreased neonatal morbidity/and mortality (measured as a composite score, “NMI”), or decreased length of neonatal stay in the hospital (NNOLOS). Secondarily, they will show an increase in gestational age at birth (GAB) and a reduction in length of neonatal NICU stay (NICULOS), compared to an unscreened historical control group.

Study Design Type: Prospective cohort study of screened pregnant women compared to a historical control.

Population: Prospective subjects are recruited from ChristianaCare’s patient population as described in the study protocol. A comparable control population will be identified from ChristianaCare’s database, as described in the study protocol. A total of approximately 10,000 women meeting the screening protocol will be identified with delivery prior to July 6th, 2018. Women will be sequentially identified retrospectively who qualify for the study based on applicable inclusion and exclusion criteria. As such cohort definition dates can only be estimated but are noted with a delivery of volume of approximately 6,000 deliveries a year, this would approximate a start date for the historical cohort of August 6th, 2016.

Intervention: Qualifying women will be screened using the PreTRM® test (Sera Prognostics, Inc.) at a large tertiary care center. Predicated upon the degree of risk based on a prespecified algorithm that includes height, weight, and measurement of two serum proteins (IBP4 and SHBG), women will be treated according to a pre-determined protocol. The outcomes of the screened cohort of women will be compared to those of the historical control group at the same tertiary care center.

Outcomes:

Co-Primary outcomes: To determine whether a cohort of women who are screened with the PreTRM® test and then managed according to a prespecified protocol will have statistically significant reductions in either (a) composite neonatal morbidity and mortality (NMI score), or (b) length of neonatal hospital stay (NNOLOS), compared to a historical control group.

Secondary outcomes: To determine whether a cohort of women who are screened with the PreTRM® test and then managed according to a pre-specified treatment protocol will have statistically significant reduction in (a) length of NICU hospital stay for critical care of neonates from time of birth up to neonatal discharge (NICULOS), or (b) a statistically significant increase in duration of gestation compared to historical controls.

3 Statement of Problem and Study

3.1 Background and Rationale

Preterm delivery, defined as delivery prior to $37^{0/7}$ weeks gestation, remains the dominant contributor to neonatal morbidity and mortality throughout the world (March of Dimes Save the Children, WHO. 2012; Mathews, Menacker, and MacDorman 2004; Anderson and Smith 2003), including up to 50% of pediatric neurodevelopmental disorders (Goldenberg and Rouse 1998). Infants born prematurely are at increased risk for a variety of long term medical complications such as respiratory, gastrointestinal, cardiovascular, and metabolic disorders (McCormick & Richardson, 2002; Saigal & Doyle, 2008). Given the tremendous medical, financial and emotional burden of preterm birth, interventions that increase the GAB of premature infants, even marginally, would profoundly impact these children, their families and the health care system.

3.2 Risk Identification

To date, our ability to identify women at risk for PTB have been limited to looking for three specific clinical circumstances in a pregnant woman: 1) Non-specific socio-economic factors (e.g. African-American race, lower socio-economic status, low BMI), 2) A history of a prior preterm birth, or 3) a short cervix on transvaginal sonography. Each of these characteristics have severe limitations as screening strategies and do not allow for the meaningful identification of the majority of at-risk pregnancies. Socioeconomic risk factors are not highly specific for preterm birth and have only demonstrated a sensitivity of 32% in a general population (Mercer, 1996). The strongest known predictor thus far for predicting preterm birth is having a prior preterm birth. As a sole risk factor in singleton pregnancy, its predictive value is limited by the fact that 40% of pregnancies occur in nulliparous women and only a minority of multiparous women will have this as a risk factor, resulting in a detection sensitivity of only 11% (Petrini, 2005). Universal cervical length screening has demonstrated to be a reasonably specific marker, though shortening of the cervix only occurs in approximately 1%-2% of the general pregnant population with at most a 6% sensitivity increase (Werner, Hamel, Orzechowski, Berghella, & Thung, 2015)(Orzechowski et al. 2014; Son et al. 2016) and has shown an AUC of only 0.61 when used in a nulliparous population at mid-trimester (Esplin et al. 2017). If meaningful change is to occur in reducing the effects of preterm birth, a more sensitive and specific assay needs to be developed and to be implemented at a point early enough in pregnancy that a rational treatment strategy can be invoked.

3.3 Study Design

We propose a prospective study where pregnant women are screened between $19^{1/7}$ - $20^{6/7}$ wks gestation using the PreTRM® test (Sera Prognostics, Inc.). A predetermined risk of sPTB $\geq 16\%$ is set as the lower limit of what constitutes elevated risk that would initiate the pre-set group of treatments as defined by a prespecified protocol. The outcomes of this cohort will be compared to a historical control at the same tertiary care center at a time in which PreTRM® testing was not available. The funder, Sera Prognostics, will

remain blinded to all clinical data until a formal communication of topline results from this analysis is made.

Additionally, a cumulative fiscal analysis of both cohorts will be covered by a separate SAP (SEAR).

The study design is illustrated in **Figure 1**.

[figure not shown]

Figure 1. Design of the AVERT study

3.4 Study Population

We intend to study the effects of serum screening on women carrying a live singleton pregnancy between $19^{1/7}$ to $20^{6/7}$ weeks gestation. Inclusion criteria and exclusion criteria were shown in the study protocol.

Prospective Tested Group: as described in the prospective cohort study design.

Briefly, prospective subjects will be enrolled during a routine prenatal visit during $19^{1/7}$ - $20^{6/7}$. Prior to screening a potential subject, the Principal Investigator (PI) will have obtained written IRB approval of the informed consent form (ICF), and other related information. Eligibility criteria are given in the protocol.

Historical Control Group: The Historical Control Group of women was defined by inclusion and exclusion criteria similar to those which defined the prospective cohort. Women who were transferred from other facilities would be excluded due to lack of records. As an exception to exclusion criteria used in the prospective cohort, women who did not meet eligibility criteria related to assay requirements were not excluded from the historical control group as these criteria are only anticipated to affect the PreTRM® test.

3.5 Primary Hypothesis or Question

Co-primary hypotheses are that women who are screened with the PreTRM® test between $19^{1/7}$ weeks and $20^{6/7}$ weeks GA will have 1) a significant reduction in severe composite neonatal morbidity and mortality (NMI), or 2) a significant reduction in length of neonatal hospital stay (NNOLOS) in comparison to historical controls.

3.6 Secondary Hypothesis or Questions

Women who were screened with the PreTRM® test will have 1) a significant reduction in length of NICU hospital stay for neonates from time of birth up to neonatal discharge or 2) a significant increase in duration of gestation (GAB) in comparison to historical controls.

3.7 Definitions of Outcomes

Primary and secondary endpoints, including adverse events, will be collected, measured, calculated, and pre-defined according to the study design.

- Composite neonatal morbidity and mortality (NMI): neonatal morbidity and mortality (14). Neonates are assigned points according to the following criteria.
0 to 4 scale with NICU
 - 0 = no events,
 - 1 = one event for (RDS, BPD, grade III or IV IVH, PVL, proven sepsis, or NEC) or <5 days in the NICU, and no perinatal mortality;
 - 2 = two events or between 5 and 20 days in the NICU, and no perinatal mortality;

3 = three or more events or >20 days in the NICU, and no perinatal mortality;

4 = perinatal mortality

The component condition abbreviations are defined as follows:

RDS: respiratory distress syndrome

BPD: bronchopulmonary dysplasia

IVH: intraventricular hemorrhage

NEC: necrotizing enterocolitis

PVL: periventricular leukomalacia

Component conditions are further defined in Appendix 1.

- Length of neonatal hospital stay (NNOLOS): days from delivery to neonatal discharge home, or until death if occurring before discharge. This includes all levels of care before discharge home, including all transfers across levels of care. NNOLOS will be calculated in fractional days if times of birth and discharge are available and rounded to the nearest integer, or as the number of days of difference between dates if times are not available; times are not required. In cases of stillbirth or neonatal mortality prior to discharge home, NNOLOS is set to one day longer than the maximum length of stay recorded for any infant. NNOLOS will be truncated at $44^{0/7}$ weeks of gestational age as specified in the protocol.
- Length of neonatal NICU stay (NICULOS): days from admission to neonatal intensive care (NICU) to neonatal discharge home from the NICU or until death if occurring before discharge. This includes all levels of care designated by ChristianaCare as intensive care, including all transfers across levels of intensive care. Nursery and non-intensive care days are not included. This will be calculated in fractional days if times of admission and discharge are available and rounded to the nearest integer value of total days, or as the number of total days in intensive care if times are not available; times are not required. NICULOS is set to zero for babies never admitted to the NICU but admitted to the hospital. In cases of stillbirth or neonatal mortality in the NICU, NICULOS is set to one day longer than the maximum length of stay recorded for any infant. NICULOS will be truncated at $44^{0/7}$ weeks of gestational age as specified in the protocol.

- Duration of gestation: GAB is set to $40^{0/7}$ weeks for deliveries on the estimated due date (EDD) and adjusted by the difference in days between the date of delivery and the EDD for all other births. The EDD is established by ultrasound data or accurately known last menstrual period (LMP), according to ACOG guidelines, as described in the protocol.

Safety outcomes: monitoring of adverse events is described in the protocol.

4. Determination of Sample Size

This study has been terminated due to the advent of the SARS-CoV-2 pandemic in the ChristianaCare population. At study termination, 1,873 subjects were enrolled in the study. To avoid bias in comparison of pre-pandemic controls to prospective subjects who reached term during the pandemic period, the primary analysis of the study will be limited to an estimated 1,453 subjects who reached $37^{0/7}$ weeks gestation before local spread of SARS-CoV-2 in Delaware and the associated shut-down of non-COVID-19 research at ChristianaCare.. Approximately 10,000 historical controls were selected from a period of about 2 years immediately prior to study initiation.

From historical data on pregnancies at ChristianaCare Health System, we estimated a historical preterm birth rate of 9.1%. The sample size estimation is based on simulations of co-primary outcomes based on a simulated distribution of gestational age with a singleton preterm birth rate of 9.1%, and an effect of intervention based on literature data²⁶⁻²⁸, with α -level spending of 0.05 shared between co-primaries using Holm's method.

Given shut-down of the study due to the SARS-CoV-2 pandemic, the sample size for the study is estimated to be approximately 1,453 subjects in the prospective arm, and approximately 10,000 in the historical control group. In the primary and alternative analyses, more than 10,000 subjects may meet the eligibility criteria for the historical control group and have the required data, and if so, they will be included in the study.

Power and sample size for this study are affected by factors including the proportion of prospective subjects receiving PreTRM® risk scores at or above the threshold of 16% risk (the study Screen Positive Rate (SPR)), the proportion of higher-risk subjects complying with interventions (compliance), and the rate at which subjects and their neonates remain in the study (retention). For the purpose of power and sample size estimation and based on study monitoring, we estimate that 34% of subjects in the pre-pandemic portion of the prospective arm had PreTRM® risk scores at or above the threshold of 16% risk (the SPR).

Power and sample size are also affected by the study population's baseline level of risk of adverse neonatal outcomes related to prematurity, the sensitivity of testing in identifying at-risk pregnancies, retention of subjects in the study and the efficacy of the interventions as implemented in the study. Literature²⁶⁻²⁸ indicates that the effect of treatment is not constant across different values of GAB. Thus, there is no single value of the effect size in terms of proportion of subjects with NMI less than 3, or mean length of stay. Rather, the effect size is larger for subjects with earlier GAB, while the effect size is reduced for subjects with later GAB.

For these reasons, power and sample size were estimated based on simulations, using a range of possible values for the factors noted above. These simulations used the observed distribution of GAB from previous studies, adjusted to match the expected overall preterm birth rate of 9.1% in this study. Treatment effect was modeled as a shift in the GAB corresponding to the effect sizes reported in published studies of preterm birth prevention that were based on single treatment modalities, and with extrapolated treatment effects estimating additive effects of bundled interventions.

For the first co-primary endpoint, reduction of severe composite morbidity/mortality, a range of the possible expected effect size can be inferred from the simulations. In the simulations, the proportion of subjects with NMI ≥ 3 is expected to be between 0.023 and 0.02 in the prospective arm and near 0.036 in the control arm based on a previous clinical utility study (Sera Prognostics: data on file). Assuming these proportions, a one-

sided Fisher's Exact test, a sample size of approximately 1,453 subjects with outcomes in the prospective arm with 55% compliance among higher risk subjects and about 10,000 historical controls provides power of 0.7 – 0.9 (NCSS PASS 2020, module "Group-Sequential Tests for Two Proportions").

For the second co-primary test, length of neonatal hospital length of stay from time of birth up to neonatal discharge is assessed by Cox proportional hazards regression with stratification. The hazard ratio based on simulations is expected to be between 1.32 and 1.46 based on a previous clinical utility study (Sera Prognostics: data on file). Assuming these hazard ratios, a sample size of approximately 1,453 subjects with outcomes in the prospective arm with 55% compliance among higher risk subjects and about 10,000 historical controls provides power of 0.8 – 1.0 (NCSS PASS 2020, modules "Group-Sequential Tests for Two Hazard Rates" and "Tests for Two Survival Curves Using Cox's Proportional Hazards Model"). Stratification is indicated based on non-proportionality observed in previous studies.

The two co-primary endpoints provide independent measurements of improved neonatal outcomes. Due to their correlation, there may be modest power to be gained from having two co-primary endpoints. The estimated study power for the combination of the two co-primary endpoints is 0.8 – 1.0.

5 Statistical Analysis

Statistical tests will be performed at the 5% significance level unless otherwise specified. Such tests will be two-tailed unless otherwise specified as directional tests. Primary and secondary endpoints will be analyzed using one-tailed tests.

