5.6 Secondary Endpoints

Reduction in length of NICU hospital stay (NICULOS) for all neonates from time of birth up to neonatal discharge in prospective subjects versus controls will be evaluated using a time-to-event analysis in the top quantile of length of stay. To avoid significant contamination of short stays associated with term births, the strata will be adjusted by the

preterm birth rate. If 1.2 times the preterm birth rate in the controls is less than 10%, the quantile will be set at 1.2 times the preterm birth rate. Otherwise the quantile will be set to 10%.

The secondary hypothesis is as follows:

H_0 : no difference between controls and the prospective arm

 NICULOS in PreTRM® test group =

 NICULOS in historical group

H_A : shorter NICULOS in the PreTRM® prospective arm as compared to historical controls.

Statistical testing for this endpoint will be performed using a Cox proportional hazards regression model with covariates and stratification as specified above.

For increase in time of gestation in prospective subjects versus historical controls, we will evaluate it using a time-to-event analysis in the bottom quantile of gestational ages at birth. To avoid significant contamination of short stays associated with term births, the strata will be adjusted by the preterm birth rate. If 1.2 times the preterm birth rate in the controls is less than 10%, the quantile will be set at 1.2 times the preterm birth rate. Otherwise the quantile will be set to 10%.

The secondary hypothesis is as follows. :

H_0 : no difference between controls and the prospective arm

 time of gestation in PreTRM® test group =

 time of gestation in historical group

H_A : longer time of gestation in the PreTRM® prospective arm as compared to historical controls.

Statistical testing for this endpoint will be performed using a Cox proportional hazards regression model with covariates and stratification as specified above.

A secondary endpoint will be met if the endpoint achieves significance with an alpha of 0.05. No adjustments will be made for the multiple hypothesis tests among the secondary endpoints, but conclusions will be interpreted with caution due to the multiple tests proposed.

Non-proportionality of secondary endpoints will be addressed using the pre-specified adjustments for non-proportionality, and the additional approaches provided above for the co-primary endpoint NNOLOS.

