The following exploratory endpoints will be evaluated using a time-to-event analysis. The null hypothesis is no difference between historical controls and the prospective arm. The alternative hypothesis is shorter length of stay in the prospective arm as compared to historical controls. Statistical testing for this endpoint will be performed using a Cox proportional hazards regression model with covariates and stratification as specified above for the primary analysis, and with propensity scoring adjustment as specified for the alternative analysis. Length of hospital stay is adjusted to the maximum observed length of stay plus one for all instances of perinatal mortality. Length of NICU stay is adjusted to the maximum observed length of stay plus one for all instances of NICU mortality.

- Reduction in length of NICU hospital stay of all NICU admissions for premature neonates. For clarity, this analysis includes only PTBs with NICU admission. This analysis will be repeated for all premature neonates delivered after spontaneous rupture of membranes or spontaneous onset of labor.
- Reduction in length of NICU hospital stay (including zero-length stays for those not admitted) for all premature neonates from time of birth up to neonatal discharge. For clarity, this analysis includes PTBs independent of NICU admission, with stays for the non-admitted set to zero days. This analysis will be repeated for all premature neonates delivered after spontaneous rupture of membranes or spontaneous onset of labor.

- Reduction in length of neonatal hospital stay for all premature neonates from time of birth up to neonatal discharge. This analysis will be repeated for all premature neonates delivered after spontaneous rupture of membranes or spontaneous onset of labor.

As exploratory analyses, the primary and alternative analyses will be replicated, with the modification that the exploratory analyses will use multiple imputation and will include the candidate variables for which more than 5% of subjects have a missing value.

As exploratory analyses, the primary analysis will be replicated as a “raw” unadjusted analysis, with the modification that no covariates will be included in regressions.

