APPENDIX I:

DEFINITIONS OF NEONATAL MORBIDITY/MORTALITY

Neonatal Death and Stillbirth: Intrauterine fetal demise at a viable gestational age or neonatal death within 28 days of delivery

Intraventricular Hemorrhage (IVH): determined by cranial ultrasound or computed tomography

Grade I	subependymal hemorrhage
Grade II	intraventricular hemorrhage, uncomplicated
Grade III	intraventricular hemorrhage with ventricular dilatation
Grade IV	intraventricular hemorrhage with ventricular dilatation and parenchymal extension

Periventricular Leukomalacia (PVL): all PVL is determined by cranial ultrasound

- Any PVL
- Cystic PVL

Necrotizing Enterocolitis (NEC)

Stage I: Other – Suspect

• Treatment was observation

Stage II: Clinical – Definite

• Treatment was medical

Stage III: Surgical – Advanced

• Treatment was surgical

Respiratory Distress Syndrome (RDS): requires both diagnosis and oxygen therapy

- For the purpose of the study diagnosis must include:
 - oxygen therapy ($\text{FiO}_2 \geq 0.40$) until infant death or ≥ 24 hours **and**
 - a clinical diagnosis of RDS

Retinopathy of Prematurity (ROP)

- Stage I Ophthalmoscopic demarcation line of normal and abnormal vessels
- Stage II Intra-retinal ridge (ridge that rises from the retina as a result of the growth of the abnormal vessels)
- Stage III Ridge with extraretinal fibrovascular proliferation (the ridge grows from the spread of the abnormal vessels and extends into the vitreous)
- Stage III+ Stage III and “plus disease” meaning that the blood vessels of the retina have become enlarged and twisted, indicating a worsening of the disease.
- Stage IV Partially detached retina.
- Stage V Complete retinal detachment.

Bronchopulmonary Dysplasia (BPD)

- Treatment with $> 21\%$ oxygen for at least 28 days, **or**
- Oxygen dependence after 36 weeks post-conceptional age

Sepsis: Must include

- Blood culture proven sepsis, **and**
- a Clinically ill infant with infection defined as:
 - Bacterial sepsis of the newborn
 - Streptococcal sepsis
 - Severe sepsis

Neonatal Seizure

- Any incident(s) documented as evidence of seizure/epileptic activity by the neonatal staff,

DEFINITIONS OF COMPOSITE PERINATAL MORTALITY/NEONATAL MORBIDITY OUTCOME SCORES:

0 to 4 scale with NICU* (NMI): This score is defined as the following:

0 = no events,
1 = one event for (RDS, BPD, grade III or IV IVH, any PVL, proven sepsis, or NEC) or <1-4 days in the NICU, and no perinatal mortality;

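### NICULOS gives its worst value only to stillbirths and deaths in the NICU, so newborns who die elsewhere before going home never receive it

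*SAP*

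**What the plan says.** SAP section 3.7 has two special rules for NICULOS. The first is for infants who stay out of intensive care: "NICULOS is set to zero for babies never admitted to the NICU but admitted to the hospital". It makes no exception for infants who die. The second is for death: "In cases of stillbirth or neonatal mortality in the NICU, NICULOS is set to one day longer than the maximum length of stay".

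The other two outcomes in section 3.7 do not depend on where the infant died. For NNOLOS: "In cases of stillbirth or neonatal mortality prior to discharge home, NNOLOS is set to one day longer than the maximum length of stay recorded". The top NMI score is "4 = perinatal mortality", and Appendix I defines the deaths as "Intrauterine fetal demise at a viable gestational age or neonatal death within 28 days of delivery", with no limit on place.

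Section 5.6 analyses NICULOS in every newborn: "Reduction in length of NICU hospital stay (NICULOS) for all neonates from time of birth up to neonatal discharge in prospective subjects versus controls". The alternative hypothesis is a shorter stay, and the analysis is confined to the top quantile of stay.

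Section 5.7 restates the death rules for the exploratory stay endpoints. For hospital stay: "Length of hospital stay is adjusted to the maximum observed length of stay plus one for all instances of perinatal mortality". For NICU stay: "Length of NICU stay is adjusted to the maximum observed length of stay plus one for all instances of NICU mortality". Stillbirth is not named in the NICU-stay sentence.

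**The concern.** The maximum-plus-one rule is there so that a death cannot pass as a short stay. In NICULOS it is incomplete. Some infants who die before going home receive a zero, an ordinary NICU stay, or no defined value, while NNOLOS and NMI count the same infants as worst.

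Two things are at stake. First, a zero is the most favourable value, so the deaths concerned normally drop out of the tail that section 5.6 analyses. If treatment turned such a death into survival with a long NICU stay, the endpoint would record a benefit as a worsening. Second, sections 3.7 and 5.7 give different instructions for stillbirth on NICU stay, so two analysts could code the same infant differently. Section 5.6 lets NICULOS be declared met at an unadjusted alpha of 0.05, so its coding should be unambiguous.

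**Working it through.** **Step 1. Apply the written rules to each kind of death.** The SAP gives no maximum stay. I assume a longest recorded NICU stay of 100 days, so maximum plus one is 101.

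| Infant | NICULOS (3.7) | NNOLOS (3.7) | NMI (3.7, Appendix I) |
|---|---|---|---|
| Stillbirth | 101 | maximum plus one | 4, if at a viable age |
| Death in the NICU | 101 | maximum plus one | 4, if within 28 days |
| Live-born, admitted to hospital, dies without entering the NICU | 0 | maximum plus one | 4, if within 28 days |
| Delivery-room death | 0 if it counts as a hospital admission, otherwise undefined | maximum plus one | 4 |
| Dies after leaving the NICU, before going home | NICU days actually spent | maximum plus one | 4, if within 28 days |

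The last row follows because section 3.7 excludes nursery and other non-intensive days from NICULOS and limits the penalty to death in the NICU. The last three rows never reach the worst NICULOS value.

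**Step 2. Place a zero relative to the analysed quantile.** Section 4 gives a historical preterm birth rate of 9.1%. Section 5.6 uses 1.2 times the control rate if that is below 10%, and 10% otherwise.

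1.2 × 9.1% = 10.92%, which is not below 10%, so the top 10% is used.

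If taken within each arm, this is 0.10 × 1,453 = 145 prospective and 0.10 × 10,000 = 1,000 control infants. A zero lies outside this set unless fewer than about 10% of infants have any NICU stay. The SAP does not give that proportion.

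**Step 3. Size.** The SAP gives no rate of death outside the NICU. I assume 0.05% to 0.3% of births.

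- Prospective: 0.0005 × 1,453 = 0.7, and 0.003 × 1,453 = 4.4.
- Control: 0.0005 × 10,000 = 5, and 0.003 × 10,000 = 30.
- Relative to the top decile: 0.0005 / 0.10 = 0.5%, and 0.003 / 0.10 = 3%. The ratio is the same if the decile is taken over both arms together.

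The SAP states no sample size or power for NICULOS, so there is no figure of its own to reproduce.

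**Step 4. Compare sections 3.7 and 5.7.** Section 3.7 gives a stillbirth maximum plus one on NICULOS. Section 5.7 raises only NICU deaths, and its endpoint for all premature neonates sets the stay of infants not admitted to the NICU to zero. Read literally, a preterm stillbirth included in that set would score zero there and the worst value under section 3.7.

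**The case against.** The strongest reply is that little depends on this. NICULOS is secondary, and section 5.6 asks for caution in interpreting it. Both co-primary endpoints count these deaths, and section 5.7 reports the components of the morbidity and mortality index descriptively. The same rule applies to both arms, and the infants are few. All of this stands, and it lowers the priority. It does not make the rule right: NICULOS still scores some deaths as the best outcome.

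A reader might also infer more than the text supports:

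- *Every delivery-room death scores zero.* The zero rule requires hospital admission, which the SAP does not define. Without an admission the score is undefined.
- *Recording a very early loss as stillbirth or live birth switches the score from worst to best.* Appendix I limits stillbirth to a viable gestational age, so a fetal loss below viability does not clearly receive the worst value. The switch needs a viable age and, for the live birth, a hospital admission followed by death without NICU entry.
- *Such an infant takes the best rank in the tail analysis.* Normally it is outside the analysed set with most other infants. The effect is the omission of a few deaths.
- *The rule favours the prospective arm.* Nothing in the SAP shows this. Equal effects cannot be assumed either: under section 5.1, higher-risk prospective women enter the modified ITT population only if they started treatment before 24 weeks, and controls face no such condition.

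**Conclusion.** The point holds as a scoring gap in a secondary endpoint. As written, NICULOS gives the worst value only to stillbirths and deaths in the NICU. An infant admitted to the hospital who dies without NICU entry scores zero, a delivery-room death scores zero or is undefined, and a death after NICU care but before going home keeps its NICU days. This departs from NNOLOS and NMI, and section 5.7 departs from section 3.7 by omitting stillbirth.

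The effect is probably small: about 1 to 4 prospective and 5 to 30 control infants, or 0.5% to 3% of the size of the top decile. These counts rest entirely on the assumed rate of 0.05% to 0.3%. The direction of bias is unknown, and no change in the study's conclusion has been shown. It should be corrected because the coding is wrong on its face and cheap to repair.

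**What to change.** In section 3.7, set NICULOS to maximum plus one for stillbirth or any neonatal death before discharge home, wherever it occurs. Limit the zero score to infants who never entered the NICU and were discharged alive. Together these cover deaths on other wards, delivery-room deaths and deaths after NICU care, and they remove the dependence on an undefined admission term for infants who die.

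In section 5.7, use the same two rules for the NICU-stay endpoint that covers all premature neonates, and name stillbirth there. For the endpoint restricted to preterm births with NICU admission, apply maximum plus one only to admitted infants who die before discharge home.

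The cost is SAP wording. No data are needed beyond those already required for NNOLOS and NMI.
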